¹ Clinical signs/symptoms suggestive of tuberculosis include: (a) Persistent cough: persistent (>2 wk), unremitting cough. (b) Weight loss/failure to thrive: (b1) Unexplained weight loss: >5% reduction in weight compared with the highest weight recorded in last 3 months OR (b2) Failure to thrive defined as (i) Clear deviation from a previous growth trajectory, and/or (ii) Documented crossing of percentile lines in the preceding 3 months, and/or (iii) Weight-for-age z score of ≤ -2 in the absence of information on previous/recent growth trajectory, and/or (iv) Weight-for-height z score of ≤ -2 in the absence of information on previous/recent growth trajectory AND (b3) Not responding to nutritional rehabilitation (or antiretroviral therapy if HIV infected). (c) Persistent unexplained fever: Persistent (>1 week) and unexplained fever (>38°C) reported by a guardian or objectively recorded at least once. (d) Persistent, unexplained lethargy or reduced playfulness: persistent, unexplained lethargy or decrease in playfulness/activity reported by the parent/caregiver. (e) Infants 0–60 day (or neonate): additional signs and symptoms suggestive of tuberculosis include: (e1) neonatal pneumonia or (e2) unexplained hepatosplenomegaly or (e3) sepsis-like illness.

² CXR will be considered consistent with tuberculosis if reviewers agree on the presence and location (right/left) of \geq 1 lesion among the following: alveolar opacity, bronchial compression, excavation, ghon focus, gibbus, miliary, nodular infiltrates, paratracheal nodes, peri-hilar nodes, pleural effusion, tracheal compression (as suggested by Graham et al. 2012 [52]).

CXRs will be read by 2 independent experts experienced in reviewing CXRs in children, blinded to all of the clinical information and to each other's interpretation. In case of disagreement, advice from a third expert will be sought.

An Expert Committee will be set up at national level for the purpose of case review and validation of TB diagnosis including causes of death in children who would die after inclusion in the study. The Expert Committee will not review all cases systematically. We will use an

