4.2. Methodology

This will be a prospective cohort study enrolling 720 children with SAM (see 4.3. Sample size).

The diagnostic strategy will include an initial clinical, radiographic and bacteriological evaluation of all enrolled children. For the purpose of the study, additional diagnostic methods will be added and evaluated including: abdominal ultrasonography, QFT IGRA, MLR, CRP as well as alternative sample collection methods (NPA, stools samples). MLR, CRP, QFT, and abdominal ultrasound findings will be made available to the clinicians. Although not currently recommended by the WHO and NTPs, these tests may contribute to patient care. Training on how to interpret tests results will be provided during the study preparation phase (see Chapter 6.2), together with specific SOPs. In particular, caution will be recommended to avoid using these tests to rule out TB.

Clinicians will make a diagnosis using national TB algorithms (referred to as "the clinician's diagnosis"). Results will be provided to the attending clinicians, i.e. not members of the study, who will make the final decision to initiate TB treatment according to current National Guidelines.

At the end of the study, children will be retrospectively classified as confirmed, unconfirmed, or unlikely TB, using the updated version of the Clinical Case Definition for Classification of Intrathoracic Tuberculosis [45] (Table 2). For model development, the reference diagnosis will be *confirmed* and *unconfirmed* TB.

Using logistic regression, we will develop a score for TB diagnosis, considering confirmed and unconfirmed TB as reference diagnosis, in hospitalized children with SAM. As a secondary objective, and in order to reduce costs, sample collection, and complexity of the diagnostic process, we will aim at developing a first-step screening score to identify children with presumptive TB who would benefit from further diagnostic testing. This will be done similarly using logistic regression with the individual predicted probability of TB dichotomized to maximise sensitivity as predicted variable. We will exclude the following tests from model development: Ultra results on microbiological samples, abdominal ultrasound, as well as CXR if possible. Both scores will be internally validated using resampling and will be incorporated in a stepwise algorithm to guide practical implementation of the screening and diagnosis process.

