7.4. Inclusion visit

After obtaining informed consent, the following procedures will be performed during the inclusion visit:

• Complete clinical evaluation

The following data will be abstracted form existing file; additional data will be collected by site investigators or study nurses

- Reason for hospitalization
- Demographic information (sex, month and year of birth)
- Physical examination including vital signs (respiratory rate, heart rate, temperature, measurement of oxygen saturation), severe dehydration, features of shock
- Clinical and anthropometric assessment of malnutrition: WHZ, MUAC, presence and severity of oedema, medical complications², danger signs³, anaemia
- Clinical assessment for other non-dietary causes of malnutrition, including identification of important comorbidities like HIV infection, intestinal infections, malaria
- Interview of parent/guardian on medical history, past and current medication and immunization (including BCG)
- HIV status (if unknown) and history of antiretroviral therapy (ART)
- TB assessment: family exposure, history and duration of symptoms in the previous 4 weeks, including cough, signs of pneumonia, fever, diarrhoea, neurological signs
- Medical imaging
 - A digitalized CXR (standard anteroposterior and lateral view) will be realized and interpreted using standardised approach
 - Abdominal ultrasonography will be systematically performed to assess the presence of intra-abdominal lymphadenopathies, splenic micro-abscesses, hepatic abscesses or ascites

Medical imaging will be performed as soon as possible and within 24 hours of inclusion to enable quick TB diagnosis. In very sick children, CXR and abdominal ultrasonography could be postponed by 2 to 3 days.

- **Blood samples** (see section 8.2.5)
 - For HIV testing (in children with unknown HIV status, using national guidelines)
 - For malaria testing (rapid test and/or thick smear)
 - For complete blood count (anaemia assessment), transaminases, and CRP
 - For the QFT assay
 - For biobanking (storage of frozen samples)
- **Bacteriological specimen collection** (see section 8.1)

Initial bacteriological specimen collection will be done as soon as possible and within 24 hours to 48 hours of stabilization by trained nurses, including:

² hypoglycemia, hypothermia, dehydration, sepsis, lethargy; skin, respiratory or urinary tract infections [53].

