8.2.2. Xpert MTB/RIF Ultra

The Ultra assay will be performed on the following samples:

- one untreated NPA (or sputum)
- one stool sample, with prior processing
- first GA out of two collected

Xpert testing will be done at the hospital laboratory on standard G4 platforms.

The Ultra assay will be carried out according to the manufacturers' guidelines and will be defined as positive, negative or invalid based on the manufacturers' recommended criteria.

Results will be interpreted as follows:

- In case of positive result for the presence of MTB (including "trace call" positive result) on any sample, the global result will be given as "MTB detected".
- In case of negativity of Ultra performed on the two samples, the global result will be given as "MTB not detected".
- In case of an invalid or error result for MTB detection, the test will be repeated if sample volumes allow for it.
- In case of rifampicin resistance detected on one or more sample, the result will be given as "MTB detected, rifampicin resistance detected". Otherwise the result will be given as "MTB detected, rifampicin resistance not detected (or indeterminate)". Children with

rifampicin resistance detected by Ultra will have culture and phenotypic DST performed on leftovers from NPA and stool (with additional samples taken if needed), and will be started on empirical MDR-TB treatment according to national guidelines.

Ultra results will be communicated by the laboratory to the nurse or clinician as soon as the result is available.

In case of TB treatment failure or poor treatment response, appropriate samples will be performed and resistance to TB drugs will be assessed using methods available on sites (phenotypic DST or line probe assays).

Leftovers of NPA, sputum, GA and stool samples will be kept at -80°C for future ancillary/substudies.

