8.4. Radiological assessment

CXR is part of the inclusion, M2 and M6 final study visit (see Table 4).

A 2-view chest radiography (anteroposterior and lateral) will be performed using standard analogue X-ray machines with digital plates, or digitalized radiography machines where possible. Clinicians will be invited to use the simplified TB-Speed CXR reading tool to interpret CXR results. This tool focus on 6 CXR features including enlarged lymph nodes, alveolar opacity of the lung tissue, airway compression, miliary, cavitation, and pleural or pericardial effusion.

Digitalized CXRs will be archived on a centralized database accessible through a secured website (the Mereva tool, as described in Chapter 10).

For the purpose of TB reference diagnosis classification, CXRs will be reviewed independently by two readers blinded to clinical and biological data to identify CXR lesions consistent with TB, as proposed in the Clinical Case Definition for Classification of Intrathoracic Tuberculosis in Children [45]. Discordant opinions will be resolved by a third reader.

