12.2. Description of the statistical analysis plan

12.2.1. Analysis of the primary endpoint

We will use logistic regression to develop diagnostic prediction models for TB. We will handle missing data using complete-case analysis, restricting analysis to those children with data available for candidate predictors, and will consider multiple imputation. We will include as candidate predictors characteristics used in previous childhood TB scoring systems and algorithms, characteristics previously described as associated with TB in children with SAM, as well as QFT and abdominal ultrasonography results. We will include as predictors CXR features as assessed by the local reader using the simplified TB-Speed CXR reading tool. We will test various duration of symptoms (>2, >3, >4 weeks) in the models and select the one with the best Akaike Information Criterion (AIC). Alternatively automated LASSO method will be used to select predictors among all study data available for the model.

We will develop different models integrating all predictors, and excluding one at a time tests that may not be available in all resource limited settings such as QFT and abdominal ultrasonography, after discussion with the expert committee. We will obtain final models by stepwise backward selection, using a threshold of 0.135 when incorporating variables with two degree of freedom (QFT: negative, positive, and indeterminate) to maximize the AIC, or 0.157 when all variables had one degree of freedom. We will perform internal validation using bootstrap resampling to quantify model optimism, i.e. the apparent performance of the model minus its true performance, which enables to adjust the model area under the receiver-operating-characteristic curve (AUROC) to its real performance.

We will compare AUROCs of models obtained and select the models with the best discriminative ability and parsimony. We will identify the predicted probability cut-off reaching a sensitivity \geq 80%. Using this cut-off, we will develop associated diagnostic scores by assigning each variable in the models to a predictive score equal to the beta coefficient.

As sensitivity analysis, we will assess diagnostic performance of the score obtained in the different countries, in children with or without HIV-infection to identify potential heterogeneity in score performances between these groups and countries.

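### Nothing requires the local chest X-ray reading, a predictor in the primary model, to be made before Ultra and QFT results are known, so its stand-alone accuracy and its weight can be overstated

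*Protocol*

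**What the plan says.** **The reading that enters the model.** Protocol 12.2.1: "We will include as predictors CXR features as assessed by the local reader using the simplified TB-Speed CXR reading tool". The accuracy and added value of that reading are also secondary objective 5b and endpoint 5. Section 8.4 names only clinicians as users of the tool: "Clinicians will be invited to use the simplified TB-Speed CXR reading tool to interpret CXR results".

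**What those clinicians are told.** Section 8.2.2: "Ultra results will be communicated by the laboratory to the nurse or clinician as soon as the result is available". Section 4.2: "MLR, CRP, QFT, and abdominal ultrasound findings will be made available to the clinicians".

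**Timing.** Section 7.4: "Medical imaging will be performed as soon as possible and within 24 hours of inclusion to enable quick TB diagnosis". It then adds: "In very sick children, CXR and abdominal ultrasonography could be postponed by 2 to 3 days". Table 4 shows the CXR, ultrasound, QFT and Ultra results all under the D3 visit.

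**Blinding of CXR readers.** It is stated for the reference reading only. Section 3.3 has two experts "blinded to all of the clinical information", and 8.4 says "CXRs will be reviewed independently by two readers blinded to clinical and biological data".

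**Reference classification.** In Table 2 (section 3.3), a positive culture or Xpert on one respiratory specimen is enough for confirmed TB, and immunologic evidence of infection is one of the criteria for unconfirmed TB.

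**The concern.** A reader who already knows a positive Ultra or QFT knows part of the reference classification, and may resolve a borderline film in that direction. The apparent accuracy of the film then partly reflects the other test. This is review bias. It differs from incorporation of CXR in Table 2, because it would arise even if CXR were not a Table 2 criterion.

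The quantities exposed are the sensitivity and specificity of CXR on its own, and the CXR coefficients in models without Ultra or QFT. Section 12.2.1 plans models that leave out QFT because it may not be available everywhere. A CXR weight learned by readers who had the QFT result may not carry over to sites that lack it.

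Abdominal ultrasound works differently. It is not a Table 2 criterion, so knowing it gives no direct route to the reference. It mainly makes the CXR and ultrasound predictors more alike.

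**Working it through.** **1. Does any section fix the order?** The 24-hour rule in 7.4 is for performing the film, not reading it, and allows postponement. NPA is an inclusion-visit sample and Ultra runs at the hospital laboratory (8.2.2), so an Ultra result can precede the reading. QFT goes to the central laboratory (8.2.4), and for some children under 5 kg or with signs of severe anaemia it is deferred to Month 1 (Table 4, note 6), so it will often come later. The order is left open.

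**2. Inputs.** The protocol gives no figure for this bias, so what follows is an illustration.
- Expected TB cases (4.3): 720 × 0.15 = 108.
- Confirmed children, from the 0.7% and 1.7% yields cited in section 1: 720 × 0.007 = 5.0 and 720 × 0.017 = 12.2, so 5 to 12. Those yields come from Xpert and culture; the protocol expects Ultra to detect more.
- Assumed: true local sensitivity s = 0.50. When a positive result is known, the reader turns a fraction f = 0.5 of otherwise negative films positive.

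**3. Sensitivity.** Let k be the share of TB cases with a *positive* result known before reading. The rise is k × f × (1 − s) = k × 0.25.
- Ultra only, every positive known early: k = 5/108 = 0.046 gives 1.2 points; k = 12/108 = 0.111 gives 2.8 points.
- QFT route alone, assuming the result is known before reading in 30 to 50% of cases and positive in 40%: k = 0.12 to 0.20 gives 3.0 to 5.0 points.
- Both routes in full, taken as independent: k = 1 − (1 − 0.046)(1 − 0.12) = 0.16 to 1 − (1 − 0.111)(1 − 0.20) = 0.29, or 4 to 7 points. This is an upper end, since it treats every positive Ultra as known first.

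**4. Specificity.** Take 80% as the true value. If 10 to 25% of false-positive films are read down when results are known negative, specificity rises by 0.20 × (0.10 to 0.25) = 2 to 5 points. If QFT is positive in 10% of non-TB children and known early in 30 to 50%, up-reading lowers it by 0.80 × 0.10 × 0.5 × (0.30 to 0.50) = 1.2 to 2.0 points. The net sign depends on which habit dominates.

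**5. A second set of assumptions.** True sensitivity 60%, specificity 70% (odds ratio 3.5). QFT positive in 40% of TB and 10% of non-TB children; Ultra positive in 10 to 50% of TB; all results known before reading.

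| Fraction of films changed | Up-reading only: sens / spec / odds ratio | Up- and down-reading: sens / spec / odds ratio |
|---|---|---|
| 10% | 62–63% / 69% / 3.7–3.8 | 59–61% / 72% / 3.6–4.0 |
| 25% | 65–67% / 68% / 3.9–4.4 | 57–63% / 75% / 3.9–5.0 |
| 50% | 69–74% / 66.5% / 4.5–5.6 | 53–65% / 80% / 4.5–7.4 |

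The odds ratio rises in every row. Specificity goes either way, and sensitivity can fall when films are also read down.

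**The case against.** Several counter-arguments have force.

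- **The reading is already standardised.** Section 10.2 has CXR interpretation entered in the CRF on standardised forms, and 17.2.2 has the country CTU monitor interpretation performance. This stands: a form exists, and the invitation in 8.4 is at most a wording mismatch with 12.2.1. But a standard format does not control what the reader knows.
- **The local reader cannot know the final class, which is assigned at the end of the study.** Largely true. Only a positive respiratory Ultra settles it early, which is why the Ultra route is small on the cited yields.
- **Most films may be read before QFT returns.** Plausible, and a reason for modest figures.
- **Other tests are not fully blinded either.** Correct. IGRA staff are blinded to clinical status (8.2.4) and the sonographer is not the treating physician (8.5), but neither is stated to be blinded to the other test results. The firm contrast is with the reference CXR readers.
- **SOPs not shown may set a reading order.** Possible; one line in 8.4 would then settle the matter.
- **Version 7.0 is dated 13/10/2021 and last inclusion is 31/12/2021.** A new entry rule reaches few children, so most of the benefit lies in the analysis of log times.

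A reader might infer a rise in sensitivity of 8 to 13 points (0.25 × 0.30 to 0.25 × 0.50 is 7.5 to 12.5). That needs a *positive* result known before reading in 30 to 50% of TB cases, which nothing in the protocol supports. Nor does the text show that the local reading contaminates the reference standard, because the Table 2 CXR criterion comes from the blinded experts.

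**Conclusion.** The point holds as a design gap with possible, not demonstrated, bias. As written, the plan lets an index test and primary-model predictor be read with knowledge of two results that feed the reference classification.

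Stand-alone CXR accuracy and the CXR weight in models without Ultra or QFT can be overstated. A reader might also infer that the added value of CXR is inflated in every model. That does not follow: where Ultra or QFT is already in the model, a contaminated reading partly duplicates it, and the gain may be unchanged or lower. A reader might likewise infer that specificity is inflated, but up-reading in non-TB children works against that.

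The size is unknown. With a true sensitivity of 50% and half of negative films turned, the rise is about 1 to 3 points through Ultra and perhaps 3 to 5 through QFT. These figures rest on up-reading alone and on assumed timing. No change in sample size follows.

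**What to change.** **Section 8.4.** Replace the invitation with a requirement. The local reader completes the TB-Speed form (the standardised CRF form of 10.2) for every D0 film, saved and time-stamped where possible before that child's Ultra and QFT results are opened. Add a field recording which results were already known. Any later reading goes in a separate field. No result is withheld or delayed for care; where the order cannot be met, the film is flagged.

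**Section 12.2.1.** State that the first saved reading is the predictor. Add a sensitivity analysis excluding films read after an Ultra or QFT result was known.

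**Films already entered.** Compare eCRF log times (10.3.1) with GeneXpert file times, and with the recorded QFT result date where there is one. The log time is only the latest possible reading time, since entry may follow the reading, so some films will be flagged needlessly.

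**Cost.** SOP and eCRF wording, one time comparison, a fixed order of data entry and some flagged films; no extra reader or procedure. Flagged films may come more often from very sick children whose imaging was postponed, so report how the excluded children differ.

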8.5. Abdominal ultrasonography

Abdominal ultrasonography will be performed by the hospital radiology department by a trained radiologist or paediatrician who is not the physician in charge of the TB diagnosis or treatment decision. Data will be collected using standardized forms. Presence of abdominal lymphadenopathy and splenic micro-abscesses, previously described as associated with childhood TB will be assessed [48], [49]. Additional signs such as hepatic abscesses, and peritoneal effusion will also be sought.

9. STUDY VIGILANCE

9.1. Definitions

> Adverse events

An "adverse event" (AE) is defined as any unfavourable, expected or unexpected sign (clinical or biological) occurring during the study in a human subject participating in the research, whether or not considered related to treatment or procedures or to participation in the study.

Serious adverse events

A "serious adverse event" (SAE) (ICH-E6 step 4. 1996) refers to any untoward medical occurrence that:

- Results in death;
- Is life-threatening (means that the subject was at immediate risk of death at the time of the event; it does not refer to an event which hypothetically might have caused death if it were more severe);
- Requires hospitalization or prolongation of existing hospitalization;
- Results in persistent or significant disability or incapacity;
- Is a congenital anomaly or birth defect.
- Is an "important medical event" (medical events, based upon appropriate medical judgment, which may jeopardize the subject or may require medical or surgical intervention to prevent one of the above characteristics/consequences). Examples: allergic bronchospasm requiring intensive treatment at an emergency room or at home, blood dyscrasias, convulsions that do not result in inpatient hospitalization.

> New fact

A new fact is defined as any safety data that could modify significantly the evaluation of the benefit/risk ratio of the research or the study product, likely to affect the safety of participants or that could modify the study product administration, the study documentation or the conduct of the study, or to suspend or interrupt or modify the protocol or similar studies.

Examples: a SAE which could be associated with the study procedures and which could modify the conduct of the study, recommendations of the IDMC, if any, where relevant for the safety of subjects.

> Severity

The severity of an AE caused by NPA collection will be graded using the "Division of AIDS table for grading the severity of adult and paediatric adverse events" (Version 2.1 – July 2017) as included in the SOPs [56].

Causality

"Causality" refers to causal relationship between a specific AE, the study intervention and any other concomitant intervention/medication

